Research involving the collection or study of existing data, documents, records, pathological specimens, or diagnostic specimens, if these sources are publicly available or if the information is recorded by the investigator in such a manner that subjects cannot be identified, directly or through identifiers linked to the subjects.

Category 5

- Research and demonstration projects which are conducted by or subject to approval of [federal] department or agency heads, and which are designed to study, evaluate, or otherwise examine (i) public benefit or service programs; (ii) procedures for obtaining benefits or services under these programs; (iii) possible changes or alternatives to those programs or procedures; or (iv) possible changes in methods or levels of payments for benefits or services under those programs.
-
-

Category 6

- Tests and food quality evaluation and consumer studies, (i) if wholesome food without additives is consumed, or (ii) If a food is consumed that contains a food ingredient at or below the level and for a use found to be safe, or agricultural chemical or environmental contaminant at or below the level found to be safe by the Food and Drug Administration (FDA) or approved by the Environmental Protection Agency (EPA) or the Food Safety and Inspection Service of the U.S. Department of Agriculture (USDA).
-

Note: To qualify for exemption, at least one must be selected

Pro00054122: A simulation study to assess whether informing physicians of out-of-pocket cost to patients and malpractice history influences ordering. - [name] View: Review Type - Exemption Category Justification

Exemption Category

1.0 * Enter Justification

Provide the IRB with information describing your study design and methods. Provide rationale for the exempt criteria chosen on the prior page. Design:

Our research team will be measuring a series of outcome measures related to physician ordering of medical imaging study through a computerized case simulation.

Baseline measure: After presentation of clinical case participants will be asked to select one of three medical imaging study options – two variations of CT scan, and no imaging. Participants have no evidence or other information to advise their selection. The selection of an initial medical imaging study is the baseline measure.

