Measure #2 – study ordered when exposed to the Canadian Head CT decision rule: Participants will be provided with information on the sensitivity, specificity, and validation studies that have supported this decision support rule. They will then be given the same imaging options to choose from as the baseline measure – two variations of CT scan, and no imaging.

Measure #3 – study ordering when exposed to malpractice data: Participants will be provided the history of all the cases where physicians were sued for not ordering a head CT scan for patients. With this information, they will be given the option to change which imaging order they would choose in the same case.

Measure #4 – study ordering when exposed to cost information: Participants will be provided information on the cost of a CT order to the patient taken from billing data from the parent institution. They will then be given the three imaging options, and asked what they would choose given

the new information.

Measure #5 – demographic information: We will be collecting basic demographic information on the participants including status (e.g. attending or trainee, military or civilian), age (scaled response not specific age), gender, and years of practice (scaled response from attending physicians).

All data will be collected during the experiment with no planned follow-up activity or engagement with the research participants. The study data, de-identified, will be secured by password in the PI's computer.

Rationale for Exempt criteria:

Simulated cases, presentation of evidence based medicine, and educational opportunities are not only part of medical culture, but are expected to take place at medical centers offering residency training programs in the United States.

Reviewing medical decision making, cost data, and discussing malpractice are topics that are well within the scope of a normal work day for a medical provider.

For these reasons, our research team asserts that there is no more risk to participants of our research study than they would encounter on any given day working in an emergency department.

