**Title: Effect of clinical decision rules, patient cost and malpractice information on clinician brain CT image ordering: A randomized controlled trial**

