**Statistical Analysis:**

Data were recorded in our intervention server, housed at the National Institutes of Health, in a Microsoft Excel spreadsheet. The data were downloaded and analyzed using SAS, ver. 9.4 (Cary, NC). In our study, because clinicians' ordering image vs. not ordering image was the main comparison of interest, CT brain modalities (with or without contrast) were grouped together and compared with the no imaging order group. To compare the clinicians' change in image ordering, McNemar test was employed and a multiple comparison adjustment was performed using Bonferroni correction. For the comparison of the demographic or other professional characteristics among different clinician groups, Chi-square test was employed to compare the proportions of categorical variables; if more than 20% of the cells had sample size less than 5, Fisher Exact test was applied instead. Analysis of Variance (ANOVA) test was used to compare the mean (standard deviation) of continuous variables.

A sample size of 155 will achieve 80% power to detect a difference in the proportion of selecting CT imaging if 30% of clinicians choose CT order in the absence of evidence and change to no imaging order when the evidence is presented and 15% of clinicians choose no imaging order in the absence of evidence and changed to CT order when the evidence is presented.

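### The SAP's 80% power at 155 clinicians is the figure for one unadjusted McNemar test; under its own Bonferroni correction over three comparisons, power is about 66%

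*SAP*

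**What the plan says.** The Statistical Analysis section of the SAP makes two statements that bear on each other.

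- On the analysis of change in ordering: "McNemar test was employed and a multiple comparison adjustment was performed using Bonferroni correction". The number of comparisons is not given, no comparison is exempted and none is named as primary.
- On sample size: "A sample size of 155 will achieve 80% power to detect a difference in the proportion of selecting CT imaging". The scenario is "if 30% of clinicians choose CT order in the absence of evidence and change to no imaging order when the evidence is presented", with 15% switching in the opposite direction. Alpha, sidedness and any allowance for multiplicity are not given.

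The number of comparisons has to be inferred. The SAP title lists three kinds of information: "Effect of clinical decision rules, patient cost and malpractice information on clinician brain CT image ordering". The protocol, under Exemption Category Justification, starts with a baseline choice at which "Participants have no evidence or other information to advise their selection". It then lists one ordering measure for each kind of information: Measure #2, "study ordered when exposed to the Canadian Head CT decision rule"; Measure #3, "study ordering when exposed to malpractice data"; and Measure #4, the same for cost.

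The protocol's Study Subjects section gives a study-wide enrolment goal of 200. Neither document links that number to the 155.

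**The concern.** A Bonferroni correction lowers the threshold each test must meet, so a sample size that gives exactly 80% power without the correction must give less with it. If 155 was worked out for one unadjusted test, the power claim describes a different analysis from the one the SAP reports.

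The false-positive rate is not at stake, because Bonferroni controls it. What is at stake is the reading of a null result. Someone told that the study had 80% power will treat a non-significant adjusted comparison as stronger evidence against an effect than it is. Because the size of the family is unstated, the per-test threshold cannot be recovered from the SAP either.

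**Working it through.** **Inputs.** From the SAP: N = 155, power 80%, switching 30% (CT to no imaging) and 15% (no imaging to CT), McNemar test with Bonferroni. Discordance is therefore pd = 0.30 + 0.15 = 0.45 and the net change is d = 0.30 − 0.15 = 0.15. Assumed, because the documents do not say: overall two-sided alpha 0.05. Inferred: k = 3 comparisons, with k = 2 and k = 6 (all pairs of the four decisions) as a range.

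**Formulae** (normal approximation for paired proportions):

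- N = [z(1 − α/2)·√pd + z(power)·√(pd − d²)]² / d²
- Power = Φ{[d·√N − z(1 − α/2)·√pd] / √(pd − d²)}

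Here √pd = √0.45 = 0.6708 and √(pd − d²) = √0.4275 = 0.6538.

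**Step 1: the SAP's own figure.** One test at two-sided 0.05:

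- N = (1.960 × 0.6708 + 0.8416 × 0.6538)² / 0.0225 = (1.3148 + 0.5503)² / 0.0225 = 154.6, rounded up to 155.
- Power at 155 = Φ[(1.8675 − 1.3148) / 0.6538] = Φ(0.845) = 80.1%.

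The stated figure reproduces exactly with no adjustment.

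**Step 2: three comparisons.** α = 0.05/3 = 0.0167, z = 2.394:

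- Power at 155 = Φ[(1.8675 − 1.6059) / 0.6538] = Φ(0.400) = 65.5%.
- N for 80% = (1.6059 + 0.5503)² / 0.0225 = 206.6, rounded up to 207.

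**Step 3: the range in k**, at overall two-sided 0.05:

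| Comparisons | Power at 155 | Power at 200 | N for 80% | Net change detectable at 155 (80% power, 45% discordance) |
|---|---|---|---|---|
| 1 (unadjusted) | 80.1% | 89.1% | 155 | 15.0 points |
| 2 | 71.1% | 82.8% | 188 | 16.5 points |
| 3 | 65.5% | 78.5% | 207 | 17.3 points |
| 6 | 55.9% | 70.5% | 240 | 18.6 points |

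**Step 4: the approximation.** Enumerating the asymptotic McNemar test at 155 gives 80.8%, 71.9%, 65.7% and 56.4% for k = 1, 2, 3 and 6. The exact McNemar test gives 61.7% for k = 3. The result does not depend on the formula.

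**Step 5: the unstated alpha.** Two other readings reproduce 155: two one-sided tests sharing 0.05, or two two-sided tests sharing 0.10. Each gives 80.1%. With three comparisons, either alpha gives 74.9%, and N for 80% is 174. Working backwards, 80% power at 155 needs a per-test two-sided alpha of 0.0496. Three such tests imply an overall alpha of 3 × 0.0496 = 0.149.

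**The case against.** The best case for the SAP is that its sentence contains no arithmetic error. It is correct for the single contrast it describes, and what is missing is specification. The 66% rests on three things the SAP does not state: two-sided tests, overall alpha 0.05 and three comparisons. Under two of the readings in Step 5 the 80% would already be aligned. The 30%/15% scenario is a net move away from CT when evidence is shown. That suits the decision rule better than a list of lawsuits over CTs not ordered, so the sentence may have been meant for one contrast. The SAP title calls the study randomised and the protocol's inclusion criteria mention group assignment, so not every clinician need contribute to every comparison. Finally, the enrolment goal is 200, where three comparisons give 78.5%, and the data had already been analysed when the SAP text was written.

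Some of this stands. The 66% is conditional and should be quoted with its assumptions, and the correction changes no test or estimate. The rest does not remove the mismatch:

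- A Bonferroni correction implies at least two comparisons. At overall two-sided 0.05, that caps power at 155 at about 71%.
- The readings that rescue 80% need exactly two comparisons and an alpha convention that neither document mentions, whereas the documents describe three kinds of information.
- If the sentence was meant for one contrast, the SAP still does not exempt that contrast from the correction.
- Splitting clinicians into groups would leave fewer than 155 per contrast, which would not raise power.
- The SAP's claim is for 155, and even 200 falls short of 80% with three comparisons.

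**Conclusion.** The concern holds. The SAP's 80% at 155 belongs to one unadjusted two-sided 0.05 McNemar test, not to the Bonferroni-adjusted analysis in the same section. With three comparisons, overall two-sided alpha 0.05 and the SAP's own switching rates, the chance of missing the planned effect in a given comparison is about 34% at 155 (100 − 65.5) and about 22% at 200 (100 − 78.5), against the 20% implied. At overall two-sided 0.05 the shortfall at 155 appears for any family of two or more; its size depends on the count. These are per-comparison figures with no allowance for incomplete responses. They apply the 30%/15% rates to every comparison, although the SAP gives rates for only one.

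A related gap is the reference decision. The protocol presents the information in sequence and lets clinicians revise their order, so each comparison could be with baseline or with the preceding decision.

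**What to change.** In the SAP's Statistical Analysis section, state the overall alpha, the sidedness, the number of comparisons in the Bonferroni family and the reference decision for each. Then restate power at the adjusted alpha, and say how 155 relates to the protocol's goal of 200. If there are three comparisons, suitable wording is:

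> With 155 clinicians, power is about 66% at two-sided alpha 0.05/3 for a comparison with 30%/15% switching (about 78% with 200); the net change detectable with 80% power at 45% discordance is about 17.3 points.

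The 80% claim can be kept only for a single unadjusted primary comparison, and only with dated evidence that it was chosen before the data were seen. The SAP reports its analysis in the past tense, so without that evidence the choice would be post hoc and the correction should stay on all comparisons.

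The cost is one or two sentences and a less favourable power figure. No extra enrolment is needed.

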3.1 Study Protocol Version: 1 Dated: 3/30/2016

3.2 Sponsor Assigned Amendment Number: Dated:

Pro00054122: A simulation study to assess whether informing physicians of out-of-pocket cost to patients and malpractice history influences ordering. - [name]

View: Study Populations - Study Subjects

Study Subjects

1.0 * Estimated Local Enrollment Goal

Enter the anticipated number of subjects to be enrolled at local site:
75

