2.0 Estimated Study-Wide Enrollment Goal

Enter the anticipated number of subjects to be enrolled at all sites:
200

3.0 * Briefly describe the setting in which the research will be conducted.

The research will be available online at an NIH website, which can be accessed by study participants at their choice of location and electronic device.

4.0 * Participant Remuneration (Payment/Academic Credit)

Will subject(s) receive remuneration?
 Yes No

5.0 * Will prospective participants be vulnerable to coercion or undue influence?

Yes No

If yes, briefly describe additional safeguards included in the protocol to protect the rights and welfare of participants likely to be vulnerable.

6.0 * Identify targeted subject population(s) involved in this research study (Note: The purpose of this question is to determine equitable selection of subjects and to identify vulnerable populations.)

Select all that apply:

Adults (18+)

Males

Females

Pregnant Women

Human Fetuses or Neonates

Minorities

Children (<18 years of age)

Prisoners

Comatose persons

Cognitively Impaired persons

- Terminally Ill persons
- Employees of the principal investigator's institution**
- Students enrolled at the principal investigator's institution
- Non-English speaking persons
- Socially/Economically disadvantaged persons
- Caregivers
- Elderly/Aged persons
- Institutionalized Individuals

7.0 * Study Population

Briefly describe the study population? (e.g. healthy volunteers, adults with Type II Diabetes, children with Asthma):
Emergency Department providers: Doctors, Nurse Practitioners, and Physician Assistants

8.0 * Describe the selection criteria (inclusion/exclusion criteria):

a. Inclusion Criteria: Regardless of assignment to group, basic inclusion criteria include:

- 1) Licensed physician or physician trainee;
- 2) Board certified, board eligible or trainee in Emergency Medicine; and
- 3) Serve as an attending physician or trainee affiliated with the Greenville Health System.

b. Exclusion Criteria: All others not meeting inclusion criteria are excluded.

9.0 * Describe recruitment procedures, including how subjects will be contacted, by whom, and how eligibility will be determined.

Participants will be contacted by the Academic Vice Chair, [name] MD, through their work email address with information about the study and a link to the website where the simulation may be completed.

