Eligibility will be determined by an employee roster provided by [name], the business operations coordinator of the Emergency Trauma Center.

Pro00054122: A simulation study to assess whether informing physicians of out-of-pocket cost to patients and malpractice history influences ordering. - [name] View: Funding and Sponsorship - Study Funding Information

Study Funding Information

1.0 * Primary Funding Source (Active or Pending)

Select primary (active or pending) funding sources for this study:
Internal Funding

Pro00054122: A simulation study to assess whether informing physicians of out-of-pocket cost to patients and malpractice history influences ordering. - [name] View: Funding and Sponsorship - Study Sponsorship

Study Sponsorship

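### The SAP's 80% power at 155 leaves out its own Bonferroni correction, and 155 is not tied to the enrolment goals of 75 and 200 or to the eligibility rules

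*SAP*

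**What the plan says.** The SAP's Statistical Analysis section compares imaging orders within clinician by McNemar's test, with a Bonferroni correction for multiple comparisons. It does not say how many comparisons there are. The sample-size paragraph that follows says: "A sample size of 155 will achieve 80% power to detect a difference in the proportion of selecting CT imaging". The inputs are that "30% of clinicians choose CT order in the absence of evidence and change to no imaging order when the evidence is presented" and that "15% of clinicians choose no imaging order in the absence of evidence and changed to CT order when the evidence is presented". Neither alpha nor sidedness is given, and the paragraph does not mention the correction.

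The protocol's exemption justification describes a baseline order followed by three information exposures: the head CT decision rule, malpractice history and patient cost. The order is asked for again after each one.

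Under Study Subjects the protocol gives two enrolment goals. Item 1.0 ("Enter the anticipated number of subjects to be enrolled at local site") is answered 75. Item 2.0 ("Enter the anticipated number of subjects to be enrolled at all sites") is answered 200. Inclusion criterion 3 in item 8.0 reads "Serve as an attending physician or trainee affiliated with the Greenville Health System", and anyone who does not meet the inclusion criteria is excluded. On recruitment, "Eligibility will be determined by an employee roster provided by" the business operations coordinator of the Emergency Trauma Center.

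**The concern.** There are two problems.

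First, the power statement describes a test that the SAP does not plan to use. If each McNemar test is judged at a Bonferroni-adjusted level, the power that matters is the power at that level, and it is below 80% at 155. A non-significant comparison would then be read as coming from an 80%-powered test when the chance of missing the assumed effect is well above 20%.

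Second, a reader cannot tell which N the power statement belongs to. The SAP uses 155, while the protocol has 75 and 200, and no visible text links them. An all-sites goal of 200 beside a local goal of 75 implies 200 - 75 = 125 participants from elsewhere. Criterion 3, the exclusion rule and the roster rule, taken literally, admit nobody from elsewhere.

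**Working it through.** **Inputs.** From the SAP: switching proportions 0.30 (CT to no imaging) and 0.15 (no imaging to CT), N = 155, power 80%, McNemar test, Bonferroni correction. From the protocol: goals of 75 and 200. Assumed: two-sided 0.05 as the overall alpha, the same 30%/15% effect for every exposure, and every analysed clinician contributing to every paired comparison.

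**Derived quantities.** Discordant total s = 0.30 + 0.15 = 0.45, with √s = 0.6708. Difference d = 0.30 - 0.15 = 0.15. s - d² = 0.45 - 0.0225 = 0.4275, with square root 0.6538.

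**Step 1: reproduce 155.** The standard unconditional McNemar formula is

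n = [z(1-α/2)·√s + z(power)·√(s - d²)]² / d².

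At two-sided 0.05: (1.960 × 0.6708 + 0.8416 × 0.6538)² / 0.0225 = (1.3148 + 0.5503)² / 0.0225 = 154.6, which rounds up to 155. The SAP's figure is therefore sound arithmetic for one unadjusted two-sided test at 0.05.

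**Step 2: power at a given n.**

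Power = Φ{[d·√n - z(1-α/2)·√s] / √(s - d²)}.

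At n = 155, d·√n = 0.15 × 12.450 = 1.8675. Unadjusted: (1.8675 - 1.3148) / 0.6538 = 0.845, so power is 80.1%. For three tests, α = 0.05/3 = 0.0167 and z = 2.394: (1.8675 - 1.6059) / 0.6538 = 0.400, so power is 65.5%.

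**Step 3: range over the unstated number of tests.** Two would cover malpractice and cost only, the pair named in the protocol's short title. Three covers each exposure against baseline. Six is all pairs of the four ordering measures (4 × 3 / 2).

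| Tests | α per test | Power at 155 | Power at 200 | n for 80% |
|---|---|---|---|---|
| 1 (unadjusted) | 0.05 | 80.1% | 89.1% | 155 |
| 2 | 0.025 | 71.1% | 82.8% | 188 |
| 3 | 0.0167 | 65.5% | 78.5% | 207 |
| 6 | 0.0083 | 55.9% | 70.5% | 240 |

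**Step 4: check without the normal approximation.** Full binomial enumeration at 155 for three tests gives 65.7% for the uncorrected McNemar statistic and 61.7% for the exact version. The formula is therefore not pessimistic.

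**Step 5: the conditional case of 75.** d·√n = 0.15 × 8.660 = 1.2990. Unadjusted: (1.2990 - 1.3148) / 0.6538 = -0.024, so power is 49.0%. For three tests: (1.2990 - 1.6059) / 0.6538 = -0.469, so power is 31.9%. By enumeration, the exact test at unadjusted 0.05 gives 42.4%.

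**The case against.** The three sizes do not contradict each other simply as numbers. One is labelled local, one all-sites, and one is a power requirement that the all-sites goal would cover: at 200, unadjusted power is 89.1%. This stands, and 155 is not an arithmetic error.

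A reader might go further and infer that only 75 clinicians are eligible, that 155 cannot be reached, and that the design therefore has 49% power. The documents do not support that. The 75 is anticipated enrolment, not a count of eligible clinicians, and the roster headcount is not given. Criterion 3 covers affiliates of the whole health system. Item 7.0 also lists nurse practitioners and physician assistants in the study population, although criterion 1 admits only physicians and physician trainees, so even the intended pool is unclear. No document plans an analysis of 75.

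The form is also one institution's ethics application, so its recruitment rules may describe the local site only. The all-sites goal and the military-or-civilian item among the demographics hint at other sites. The multi-site selections cannot be read in the available text, and the separately uploaded protocol file is not reproduced, so a missing second site here does not prove that none was planned. What remains is that the eligibility text as written has no provision for other sites, and no visible text links 155 to 200. An allowance for incomplete sessions could explain the difference, but none is stated.

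On alpha, one could argue that 155 already includes some adjustment, since a one-sided 0.05 split over two tests gives the same critical value. Nothing in the SAP indicates one-sided testing or two comparisons, so this remains a possibility that the sample-size paragraph should settle.

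**Conclusion.** The point holds in two parts. The stated 80% at 155 is the power of a single unadjusted two-sided test at 0.05, not of the Bonferroni-corrected tests that the SAP specifies. At the corrected level it is about 71%, 66% or 56% for 2, 3 or 6 comparisons, with 66% for the natural count of three. Even 200 analysed clinicians would give only 78.5% for three tests. These figures rest on two-sided 0.05, which is inferred because it returns 155; on the 30%/15% effect applying to each exposure; and on every analysed clinician contributing to each comparison.

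Separately, 155 is not connected to either enrolment goal, and the eligibility and roster text does not fit an all-sites goal well above the local one. This is an inconsistency to reconcile. It does not show that recruitment is capped at 75. The 49% and 32% apply only if the study is local-only and the local forecast is what is achieved.

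**What to change.** 1. State one planned analysed N in both documents, and say how it relates to 75 and 200, including any allowance for incomplete sessions.
2. In the SAP, give alpha, sidedness and the number of comparisons under the Bonferroni correction, and restate power at the adjusted level: for example, about 66% at 155 for three tests. If 80% is to be kept for three tests, the same inputs require 207 analysed clinicians.
3. Reconcile inclusion criterion 3, the exclusion rule and the roster rule with the all-sites goal, either by admitting clinicians from other sites or by confirming a local-only study. Settle at the same time whether nurse practitioners and physician assistants are eligible.
4. If the study is local-only and 75 remains the forecast, report power at 75 (about 49% unadjusted, about 32% for three tests) as that scenario.

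Items 1, 2 and 4 are wording changes to the SAP sample-size paragraph and the enrolment items, and item 3 is wording in the eligibility text. The cost is a less favourable stated power, or a larger recruitment target if 80% is to be kept.
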